Based on data and assumptions used for sample size estimation (mean=-80.2mmHg, SD=14.8), a minimum of 55 subjects are required to achieve 80% power to detect equivalence at the significance level of α = 0.025 within

CONFIDENTIAL AND PROPRIETARY

Study Protocol—Device	Smith-Nephew
and performance of PICO 14 in the	Number: PICO14.WND.PRO.2019.03
	Version: 2.0, 12Sep2021
	Page: Page 102 of 131

6mmHg using a two one-sided t-test (TOST) approach. Drawing from past experience, it is expected that approximately 20% of the subjects may be lost to follow up by the end of the study and therefore to account for this N=70 subjects will be recruited into this study. This will allow for a minimum of 10 subjects with each of the following indications to be recruited: Chronic open wounds (pressure ulcers, venous leg ulcers and diabetes-related foot ulcers), dehisced surgical wounds and closed surgical incisions (post-operative incisions following hip or knee arthroplasty).

The sample size was estimated using SAS V9.4.

12. ADVERSE EVENTS AND DEVICE DEFICIENCIES.

12.1 DEFINITIONS.

The categories of adverse events are shown in table 12.1-1. The definitions for each of these categories are given in the subsequent sections. Table

12.1-1: Categories of Adverse Event

	NOT DEVICE-RELATED	DEVICE- OR PROCEDURE- RELATED	
Non-Serious	Adverse Event (AE)	Adverse Device Effect (ADE)	
Serious	Serious Adverse Event (SAE)	Serious Adverse Device Effect (SADE) (See 12.1.3)	
		Anticipated	Unanticipated
		Anticipated Serious Adverse Device Effect (ASADE)	Unanticipated Serious Adverse Device Effect (USADE)

CONFIDENTIAL AND PROPRIETARY

Study Protocol—Device	Smith-Nephew
and performance of PICO 14 in the	Number: PICO14.WND.PRO.2019.03
	Version: 2.0, 12Sep2021
	Page: Page 103 of 131

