CONFIDENTIAL AND PROPRIETARY

Study Protocol—Device	Smith-Nephew
and performance of PICO 14 in the	Number: PICO14.WND.PRO.2019.03
	Version: 2.0, 12Sep2021
	Page: Page 36 of 131

5. OBJECTIVE(S).

5.1 PRIMARY OBJECTIVE.

To assess the functional clinical performance of PICO 14 NPWT system over 14 days therapy through the verification of delivery of negative pressure and wound exudate management.

5.2 SECONDARY OBJECTIVES.

Closed incisions ONLY

To assess clinical efficacy and safety of the PICO 14 NPWT system within 30 days of surgery through:

- Incidence of Surgical Site Infection (SSI) Superficial, deep. [CDC criteria].
- Incidence of Surgical site Complications (SSC) [as applicable: dehiscence (superficial/deep etc.), seroma, necrosis, hematoma, suture abscess].
- Condition of peri-wound skin assessed through visual inspection at 7, 14 and 30 days.
- Any pain experienced by the subject in relation to the PICO 14 system.
- Patient tolerability assessed by level of pain and level of satisfaction.
- Clinician acceptability assessed by ease of application and removal.
- Dressing wear time, dressing change frequency and dressing conformability.
- Scar quality measured by Patient and Observer Scar Assessment Scale (POSAS) score.

Chronic Wounds and dehisced surgical wounds ONLY

To assess clinical efficacy and safety of the PICO 14 NPWT system within 28 days therapy period through:

- Incidence of infection.
- Condition of peri-wound skin assessed through visual inspection at 7, 14, 21 and 28 days.
- Any pain experienced by the subject in relation to the PICO 14 system.

CONFIDENTIAL AND PROPRIETARY

Study Protocol—Device	Smith-Nephew
and performance of PICO 14 in the	Number: PICO14.WND.PRO.2019.03
	Version: 2.0, 12Sep2021
	Page: Page 37 of 131

Wound assessment:

- Appearance of the wound.
- Level of exudate.
- Wound pain.
- Size of wound (percentage reduction in area, depth, and volume).
- Patient tolerability assessed by level of pain and level of satisfaction.
- Clinician acceptability assessed by ease of application and removal.
- Dressing wear time, dressing change frequency and dressing conformability.

5.3 OTHER OBJECTIVES.

No other objectives.

5.4 SAFETY.

To assess Adverse Events and Device Deficiencies.

5.5 CLAIMS.

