8.5 RETENTION PERIOD

All eCRFs will be archived once the study is completed and will kept for a period of no less than five years after the later of the following dates: the date of which the study is terminated or completed or; the date that the records are no longer required supporting marketing applications.

8.6 STUDY ENDPOINTS.

8.6.1 PRIMARY ENDPOINT.

Functional clinical performance of the PICO 14 NPWT system over the treatment period to include:

- Delivery of -80mmHg negative pressure to the wound bed over the treatment period. This
 will be measured by download of the built-in data chip from the PICO 14 devices to collect
 NPWT delivery status.
- Exudate management assessed by no occurrence of exudate leaks during the treatment period resulting, or not, in an unplanned dressing change.

8.6.2 SECONDARY ENDPOINTS.

Closed Incisions Only:

Clinical performance and safety of the PICO 14 NPWT system over a 14 day therapy and 30 day follow-up period to include:

- Scar quality measured by POSAS score at Day 14, and day 30.
- Incidence of Surgical Site Infection (SSI) and incidence of Surgical Site Complication (SSC) within 30 days of surgery [CDC criteria].
- Condition of peri-wound skin assessed through visual inspection at 7, 14 and 30 days.
- Level of pain on application, during wear and at dressing removal assessed by VAS scale over the 14 day treatment period.
- Patient satisfaction during wear assessed over the 14 day period. This includes leakage, feeling of moisture on the skin, odour control, level of protection, comfort and showerproof qualities.
- Ease of application and removal of the PICO 14 dressing.

CONFIDENTIAL AND PROPRIETARY

Study Protocol—Device	Smith-Nephew
and performance of PICO 14 in the	Number: PICO14.WND.PRO.2019.03
	Version: 2.0, 12Sep2021
	Page: Page 55 of 131

- Dressing wear time.
- Dressing conformability
- Dressing change frequency and reason for dressing change.
- Clinician acceptability of PICO 14 system at discontinuation of therapy.
- Patient acceptability of PICO 14 system at discontinuation of therapy.

Chronic wounds and dehisced surgical wounds only:

Clinical performance and safety of the PICO 14 NPWT system over a 28 day therapy and no follow-up period to include:

- Incidence of clinical infection
- Appearance of the wound in terms of, tissue type and amount, exudate type and amount, skin condition surrounding the wound, peripheral tissue edema and induration,

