The subjects will be described and summarised using the baseline demographic and medical variables which include but are not limited to age, gender, ethnicity, medical and medication history, diagnostic factors. Summary statistics will be given according to the nature of the variable; continuous or categorical.

11.4 EFFICACY ANALYSIS.

The study will assess and evaluate the efficacy of PICO 14 by establishing equivalence in the mean operating negative pressure over a period of 14 days with a pressure of -80.2 mmHg. The clinical efficacy of PICO 14 will be concluded if statistically significant equivalence (within an equivalence margin of ±6mmHg) is achieved. Secondary and exploratory outcomes will be evaluated to consolidate the primary outcome analysis.

The study is non-comparative and non-randomised, the impact of confounding on the measures of efficacy may be expected and will be evaluated through fitting appropriate models and adjusting for potential factors.

11.5 ANALYSIS OF PRIMARY ENDPOINT.

Delivery of -80mmHg negative pressure to the wound bed over the treatment period. This will be
measured by download of the built-in data chip from the PICO 14 devices to collect NPWT delivery
status.

The following hypotheses will be tested to establish equivalence of the PICO 14 integrated pump system compared to the literature value, with equivalence margin, δ_1 >0:

$$H_0: |\mu - \mu_0| \ge \delta_1$$

$$H_a$$
: $|\mu - \mu_0| < \delta_1$

In the stated hypotheses, μ represents the assumed mean operating pressure taken from data extracted from a PICO sample device (-80.2 mmHg) and μ_0 represents the mean PICO 14 pump operating pressure.

CONFIDENTIAL AND PROPRIETARY

Study Protocol—Device	Smith-Nephew
and performance of PICO 14 in the	Number: PICO14.WND.PRO.2019.03
	Version: 2.0, 12Sep2021
	Page: Page 96 of 131

The equivalence limit δ_1 = 6mmHg was chosen as a conservative non-clinically significant difference assuming that the difference is actually 0.

The average negative pressure across all subjects will be summarised as a continuous variable.

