The difference between the average negative pressure from baseline to treatment discontinuation and the assumed mean negative pressure (-80.2mmHg) will be calculated for each subject separately. This difference for closed incisions, dehisced surgical wounds and chronic wounds combined will be assessed using a two one-sided t-test at the alpha level of 0.025. The mean difference will be presented along with the associated 95% confidence interval and if the 95% confidence interval lies fully within the equivalence boundaries (-6; 6) then the null hypothesis is rejected and clinical equivalence will be confirmed.

As an additional analysis the above will be repeated separately for each wound indication.

 No occurrence of exudate leaks observed during the dressing wearing period resulting or not, in an unplanned dressing change.

Occurrence of exudate leaks in the opinion of the clinician will be recorded in the CRF. For non-occurrence of exudate leaks, a binary variable indicating presence of/absence of will be defined. For the combined group (closed surgical incisions, dehisced surgical wounds and chronic wounds) the frequency together with percentage of reported/identified outcome will be reported with a 95% CI. This will also be summarised separately for each wound indication.

Logistic models will be fitted and important associated factors adjusted for if there is adequate data.

Composite Clinical Success (CCS) defined as a binary variable (1/0) (1 if both of the following are true and 0 if either one is false):

- A. Nominal pressure is in the interval 80mmHg ± 6mmHg.
- B. No exudate leakage.

The CCS will be reported as a count and percentage with a 95% CI for the combined group and separately for each wound indication.

CONFIDENTIAL AND PROPRIETARY

Study Protocol—Device	Smith-Nephew
and performance of PICO 14 in the	Number: PICO14.WND.PRO.2019.03
	Version: 2.0, 12Sep2021
	Page: Page 97 of 131

11.6 ANALYSIS OF SECONDARY ENDPOINTS.

Closed Incision Only:

Clinical performance and safety of the PICO 14 NPWT system over a 14 day therapy and 30 day follow-up period to include:

- Scar quality measured by POSAS score at Day 14, and day 30.
- Incidence of Surgical Site Infection (SSI) and incidence of Surgical Site Complication (SSC) within 30 days of surgery [CDC criteria].
- Condition of peri-wound skin assessed through visual inspection at 7, 14 and 30 days.

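### Section 11.4 concludes clinical efficacy from mean-pressure equivalence alone, with no role for exudate leaks or for the outcomes that 5.2 itself calls efficacy

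*Combined protocol and SAP*

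**What the plan says.** Section 5.1 sets the primary objective as functional clinical performance, assessed "through the verification of delivery of negative pressure and wound exudate management". Section 8.6.1 lists two matching components of the primary endpoint. One is delivery of −80 mmHg, read from the pump's data chip. The other is: "Exudate management assessed by no occurrence of exudate leaks during the treatment period resulting, or not, in an unplanned dressing change". The synopsis has the same two parts.

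Section 11.4 begins: "The study will assess and evaluate the efficacy of PICO 14 by establishing equivalence in the mean operating negative pressure", with −80.2 mmHg over 14 days as the reference. The decision rule follows: "The clinical efficacy of PICO 14 will be concluded if statistically significant equivalence (within an equivalence margin of ±6mmHg) is achieved". The next sentence adds: "Secondary and exploratory outcomes will be evaluated to consolidate the primary outcome analysis".

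Section 11.5 gives a hypothesis and a confidence-interval criterion for pressure. For leaks in the combined group, "the frequency together with percentage of reported/identified outcome will be reported with a 95% CI". Leaks are also summarised by wound indication, with logistic models if the data suffice. The section then defines CCS as a per-subject success that needs both "Nominal pressure is in the interval 80mmHg ± 6mmHg" and no leakage. On its reporting: "The CCS will be reported as a count and percentage with a 95% CI for the combined group and separately for each wound indication".

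Section 5.2 uses the term clinical efficacy and safety for the secondary objectives. These include surgical site infection and surgical site complications for closed incisions, and infection and wound size for chronic and dehisced wounds.

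**The concern.** A decision rule that ends in a claim of clinical efficacy should depend on whatever the plan treats as evidence of efficacy. This one depends only on the mean of the subjects' average pressures. One of the two primary components cannot alter the conclusion in either direction, and neither can the clinical outcomes in 5.2.

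What is at stake is the wording of the headline result. Under section 5.5 the study report feeds the clinical evaluation report on safe and effective use, in support of continued CE marking. An efficacy statement taken from 11.4 could be challenged there against the protocol's own objectives.

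**Working it through.** **1. The plan's own numbers.** The only sizing (11.10) is for the pressure test: at least 55 subjects, raised to 70 for about 20% loss. The loss step reproduces: 55 / (1 − 0.20) = 68.75, so at least 69, and 70 covers it. Nothing is sized for leaks or CCS. I use 55 only as a denominator. Whether 55 gives the stated power is a separate question that this point does not need.

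**2. Role of each outcome.**

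| Outcome | Status in the plan | Planned analysis | Role in the 11.4 conclusion |
|---|---|---|---|
| Mean pressure | Primary (5.1, 8.6.1) | Two one-sided t-tests; 95% CI within ±6 mmHg (11.5) | Sufficient alone |
| Exudate leaks | Primary (5.1, 8.6.1) | Percentage with 95% CI; no criterion (11.5) | None |
| CCS | Not listed in 8.6 | Count and percentage with 95% CI; no criterion (11.5) | None stated |
| Infection, complications, wound size | Secondary; under efficacy and safety in 5.2 | Summaries; signed-rank test for reduction in area and volume (11.6) | May consolidate; no condition set |

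**3. The rule as a formula.** Let (L, U) be the 95% CI for the mean difference from −80.2 mmHg, and let k be the number of leak-free subjects. Section 11.4 concludes efficacy if L > −6 and U < 6. The count k does not appear, so for given pressure data the conclusion is the same for every k from 0 to n.

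**4. Illustration at n = 55.** The counts are my examples. The plan does not name a CI method, so I assume the exact (Clopper–Pearson) interval: lower limit = Beta quantile(0.025; k, n − k + 1), upper limit = Beta quantile(0.975; k + 1, n − k).

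| Leak-free k of 55 | Proportion | Exact 95% CI | 11.4 conclusion if L > −6 and U < 6 |
|---|---|---|---|
| 55 | 100% | 0.935–1.000 | Clinical efficacy |
| 44 | 80% | 0.670–0.896 | Clinical efficacy |
| 11 | 20% | 0.104–0.330 | Clinical efficacy |

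Check on the first row: with k = n the lower limit is 0.025^(1/55) = 0.935.

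This step needs no assumption about the distribution of pressure.

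**5. Scope elsewhere.** Section 11.10 describes the same test as one of equivalence in mean operating pressure. In 11.5 the words clinical equivalence sit inside the pressure paragraph. Only 11.4 widens the result to clinical efficacy.

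**The case against.** The strongest reply is that 11.5 already deals with leaks. It analyses them under the primary endpoint with a confidence interval, overall and by indication, and adds a composite that requires both pressure and no leakage. A report that follows section 11 must show these results. This stands: a reader might infer that leaks are unanalysed or could be concealed, and the documents do not support that.

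A second reply is that section 11 calls itself a brief description and promises a more detailed SAP. That limits the point to the text as written. It does not answer it, because the rule is explicit and is what the SAP would inherit.

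A third is that the sentence on consolidation covers other outcomes. It names secondary and exploratory outcomes. It might be read to include CCS, but leaks are primary, and it sets no condition for any outcome.

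A fourth is that a leak may lower the recorded pressure and so enter the test indirectly. That is possible, which is why the comparison holds the pressure data fixed. The plan nevertheless records leaks separately, on the clinician's opinion.

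Finally, section 11 uses efficacy loosely, as in the heading of 11.4 and the objectives named in 11.2. That may explain the wording. But a heading is a label, whereas the sentence at issue states what will be concluded.

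**Conclusion.** The 11.4 conclusion is wrong as written: it names a result wider than the test behind it. The mismatch is twofold. The rule omits half of the primary objective, and it uses a term that 5.2 attaches to secondary clinical outcomes. Adding leaks would therefore not turn the result into clinical efficacy either, since 5.1 speaks of functional clinical performance.

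The size of the problem is structural: for fixed pressure data, no leak result changes the statement. This rests on the text of 11.4 alone; the leak counts and the interval method only illustrate it.

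Three stronger readings are tempting and are not supported:

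- **That the plan must test leaks or CCS against a threshold.** Descriptive reporting is a legitimate choice in a single-arm case series, and the documents give no threshold.
- **That 11.5 and 11.10 make the same error.** Their claims already sit within pressure text.
- **That a passing trial would have some particular low share of subjects within 80 ± 6 mmHg.** The documents do not say that the SD of 14.8, taken from a sample device, is a between-subject SD. They do not define nominal pressure for CCS either.

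**What to change.** Change 11.4 only:

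- In the decision sentence, make the main clause read: *Equivalence in mean operating pressure will be concluded*, and keep the condition that follows.
- In the sentence before it, replace *efficacy* with *pressure delivery*.
- Add: *Any conclusion on the primary objective will present the pressure result together with the leak-free proportion and CCS with their 95% CIs (11.5).*

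Carry the same wording into the SAP, which is to be finalised before database lock. Sections 11.5 and 11.10 need no edit for this point.

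The cost is a few words in one paragraph. No threshold, test, data or subjects are added and power is unaffected. The downside is that the sponsor can claim less from the pressure test.

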Data generated from the study will populate a clinical study report which will feed into the clinical evaluation report for PICO 14 to evaluate the safe and effective use of the PICO 14 system in chronic open wounds and closed surgical incisions, and support part of the PMCF plan for this product, for the purpose of continuing CE (Conformité Européene) Mark approval in accordance with MEDDEV 2.12-2.

6. INVESTIGATIONAL PRODUCTS.

6.1 IDENTIFICATION.

6.1.1 INVESTIGATIONAL PRODUCT.

CONFIDENTIAL AND PROPRIETARY

Study Protocol—Device	Smith-Nephew
and performance of PICO 14 in the	Number: PICO14.WND.PRO.2019.03
	Version: 2.0, 12Sep2021
	Page: Page 38 of 131

PICO 14 is a single-use Negative Pressure Wound Therapy System consisting of a small portable pump, 2 AA batteries, 2 dressings and fixation strips. The PICO 14 pump maintains NPWT at 80 mmHg (nominal) to the wound surface. Exudate is managed by the dressing through a combination of absorption and evaporation of moisture through the outer film. The PICO 14 dual dressing kit is intended to be used for up to 14 days on low to moderately exuding wounds. The frequency of dressing changes can be affected by multiple factors such as wound type, wound size, rate or volume of exudate, orientation or environmental conditions. Additional dressings will be provided as required.

PICO 14 may be used in a hospital or community setting and is indicated for acute and chronic, sub-acute, dehisced and traumatic wounds, flaps and grafts, surgically closed incision sites, and partial thickness burns. For this study, PICO 14 will be used to manage post-surgical wounds closed by primary intention, chronic wounds and dehisced surgical wounds as defined in the study eligibility criteria. PICO 14 is also used on chronic wounds such as Venous Leg ulcer, Arterial Leg Ulcer and Diabetic foot Ulcer and pressure ulcers. This is due to the PICO 14 pump capability of providing therapy for 14 days. PICO 14 will be applied for 14 days (for closed incisions only) with a dressing change at 7 days on low exuding wounds. For moderately/high exuding wounds each PICO dressing can be used for up to 4 days.

Please note for chronic and dehisced surgical wounds PICO 14 may be applied for up to 28 days by using two PICO 14 systems for treatment.

PICO 14 is manufactured by Smith+Nephew Medical Limited, [name]. PICO 14 is packed in the UK with individual components made in the following countries:

- Dressing UK.

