management of acute and chronic wounds	Page: Page 47 of 131

If the subject or the legally designated representative (if applicable) does not give consent, the subject or legally designated representative will be informed of the right to object to the use of data obtained from the clinical investigation.

If new information becomes available during the course of the study that can significantly affect a subject's future health and medical care, Smith + Nephew will ensure that information shall be provided to the subject(s) affected in written form and if relevant, all affected subjects shall be asked to confirm their continuing consent in writing.

7.6 ENROLLMENT.

Enrolment in this study shall occur at the point the consent process has been completed and study number is allocated to the subject.

7.7 LOST TO FOLLOW-UP.

A subject will be considered lost to follow-up if he/she does not appear for the scheduled study visit for 2 consecutive visits and does not return for a final visit, and study personnel are unable to contact the subject.

Some actively enrolled subjects will not return for follow-up exams on time. Study personnel must make a reasonable effort to contact the subject and document the following contact attempts before declaring a subject to be lost to follow-up: the subject has been contacted according to the site's policies, but no fewer than two documented phone contacts and one certified letter without response. Copies of all attempts to reach the subjects by mail or email and/or the attempts to contact the subject via other means should be documented, and that documentation should be kept with the subject's source documents.

CONFIDENTIAL AND PROPRIETARY

Study Protocol—Device	Smith-Nephew
and performance of PICO 14 in the	Number: PICO14.WND.PRO.2019.03
	Version: 2.0, 12Sep2021
	Page: Page 48 of 131

7.8 WITHDRAWAL.

7.8.1 WITHDRAWAL OF TREATMENT.

Subjects may be withdrawn early from study treatment for the following reasons:

- Subject does not return following treatment (and pump is lost).
- Treatment is prematurely ended for any reason (i.e. due to removal of the system by the subject, failure of the pump, dressing falls off, seal can no longer be established).
- Treatment is disrupted for longer than 24 hours (i.e. airtight seal was disrupted and was not re-established with a 24 hour time period).
- At the discretion of the Investigator due to:
 - A change in treatment is clinically warranted (to include further treatment following

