9.1.3 DAY 7 (-3 DAYS) FOLLOW UP DRESSING INSPECTION

- Record date and treatment setting. If outpatient, record date of previous discharge.
- 2. If therapy is being discontinued prior to 7 days or dressing is no longer in place, complete the End of Therapy Assessment (9.1.6 below).
- 3. Record if therapy has been interrupted since the previous assessment and how long.
- 4. Record the use of concomitant medications.
- 5. Take photograph of dressing in place.
- 6. Assess subject comfort (yes, no) and pain level (Visual Analogue Scale).
- 7. If dressing change is required then please follow additional dressing study procedures.
- If any adverse device effects or device deficiencies are observed or reported, they
 must be recorded as instructed in Section 12 Adverse events and device
 deficiencies.
- 9. Instruct the subject on follow-up procedures, including returning to the treatment facility for the End of Therapy Assessment Visit at 14 (-2) days post-surgery.

9.1.4 END OF THERAPY ASSESSMENT DAY 14 (-2) DAYS.

- 1. Record date and treatment setting. If outpatient, and not previously recorded, record date of previous discharge.
- 2. If therapy is being discontinued prior to 14 days, record reason (e.g. PICO 14 NPWT system removed, treatment interrupted for 48 hours or more, clinician recommends a change in treatment, at the discretion of the Investigator, adverse event, subjects own request, lost to follow-up, other). If pump is faulty change is permissible during therapy period record the reason under Device deficiency CRF form.
- 3. Record the use of concomitant medications.

CONFIDENTIAL AND PROPRIETARY

Study Protocol—Device	Smith-Nephew
A prospective, study to evaluate the safety and performance of PICO 14 in the management of acute and chronic wounds	Number: PICO14.WND.PRO.2019.03
	Version: 2.0, 12Sep2021
9	Page: Page 61 of 131

- 4. Record reason if dressing is no longer in place (e.g. pain/discomfort from the dressing, patient removed, patient's request, adverse event, no vacuum, pump turned off, reason for dressing change and exudate management data collection, other).
- 5. Take photograph of dressing in place.
- 6. Record if therapy has been interrupted since the previous assessment and how long.
- 7. Assess subject satisfaction (overall performance of dressing, comfort, noise level, discreteness, portability, interference with daily living showering, sleeping, socialising, working).
- 8. Remove NPWT system as per procedure (section 9.2.4).

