- Level of pain from the incision since the last assessment (0-10 scale).
- Reason for dressing change (Routine/ inadequate exudate management / pain-discomfort from the dressing / dressing damaged / dressing fell off / patient removed dressing / adverse event / surgical procedure / safety alarm / dressing components not in place / no vacuum /other).
- Is the dressing still covering the incision as applied? (Yes / No).
- How long has the dressing not covered the incision? (Day / Hour / Min) if applicable.
- Has the dressing been removed at any point since application? (Yes / No).
- How long was the dressing not in place? (Day / Hour / Min).
- Has there been any period that the vacuum was not applied during therapy apart from showering? (Yes / No. If yes, for how long).
- Level of Pain on removal of dressing (0 -10 scale).
- Was the dressing easy to remove? (Yes / No. If no, please comment).

9.2.6 TREATMENT DISCONTINUATION.

Treatment discontinuation information to be collected include the following questions:

- Date of treatment discontinuation.
- Reason for treatment discontinuation (End of treatment period (14 days) / Vacuum interrupted for > 48 hours / A change in treatment is clinically warranted / Subject withdrawn—Adverse Event / Other (specify). If Incision management complete.
- Overall subject assessment of PICO 14:
 - How was the pump carried around (Pump Clip / Pocket / Hand / Other? If other, please state).
 If the Pump Clip used, was the clip a useful feature (Yes/No. If No, why).
 - Subject satisfaction with the following aspects of the NPWT system: Overall performance,
 Comfort during wear, Noise Level, Discreetness, Portability (Scale).

CONFIDENTIAL AND PROPRIETARY

Study Protocol—Device	Smith-Nephew
and performance of PICO 14 in the	Number: PICO14.WND.PRO.2019.03
	Version: 2.0, 12Sep2021
	Page: Page 73 of 131

- Interference with daily living Showering, Sleeping, Socialising, Working (Yes, please comment/ No)
- Overall investigator assessment of PICO 14:
 - Overall is the Investigator satisfied with the performance of the PICO 14 system (pump and dressing) (Yes / No. If No please comment).
 - Following questions will be asked: "Are you satisfied with the PICO 14 systems ability to manage wound/ incision?", Are you satisfied with the PICO 14 systems ability regarding dressing retention?" and "Are you satisfied with the PICO 14 systems ability when compared to other NPWT devices?"

9.2.7 SUBJECT EXIT.

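### Pressure delivery is judged only by each subject's time average and composite criterion A has no subject-level definition, so a long vacuum loss can score as success, mainly in 28-day wounds

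*Combined protocol and SAP*

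**What the plan says.** Section 8.6.1 makes delivery of the target pressure throughout therapy part of the primary endpoint, read from the pump's data chip. Section 11.5 analyses, for each subject, the "difference between the average negative pressure from baseline to treatment discontinuation and the assumed mean negative pressure" of -80.2 mmHg, and tests the mean of these differences by TOST with a 6 mmHg margin.

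Section 11.5 then defines Composite Clinical Success as a yes/no variable. One condition is absence of exudate leakage. The other, criterion A, is: "Nominal pressure is in the interval 80mmHg ± 6mmHg". Nominal pressure is not defined for a subject. In section 6.1.1 the word describes the pump's rating: "The PICO 14 pump maintains NPWT at 80 mmHg (nominal) to the wound surface".

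Interruptions are recorded. The visit procedures in 9.1 and 10.1 ask whether therapy was interrupted and for how long. The dressing removal forms in 9.2.5 and 10.4.6 ask: "Has there been any period that the vacuum was not applied during therapy apart from showering", with the duration. Section 11 uses none of these durations.

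The documents give more than one interruption figure. Section 7.8.1 lists "Treatment is disrupted for longer than 24 hours" under a permissive heading, "Subjects may be withdrawn early from study treatment for the following reasons". Sections 9.1.4 and 10.1.4 give "treatment interrupted for 48 hours or more" as a reason for stopping therapy, and the discontinuation forms in 9.2.6 and 10.4.7 give "Vacuum interrupted for > 48 hours".

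**The concern.** The endpoint concerns pressure sustained over the therapy period, and an average cannot show that. A complete loss of vacuum is diluted by the remaining hours, and the longer the therapy, the longer the loss that can be absorbed. The minimum and maximum promised in section 11.1 would be taken across the subjects' averages, so they do not show gaps within a subject.

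At stake is what the study can claim. The mean-pressure result and the composite could both support satisfactory delivery while some subjects had a day or more without therapy. The protocol itself treats continuity as relevant: its literature summary (4.2) credits an early PICO prototype with keeping pressure within therapy limits almost without a break.

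**Working it through.** The plan gives no figure for how much vacuum loss its average tolerates, so there is nothing to reproduce. The limits below follow from its own numbers. Pressures are shown without the minus sign.

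**Inputs from the protocol**
- Criterion A interval: 80 ± 6, that is 74 to 86 mmHg (11.5).
- Therapy length: 14 days = 336 h for closed incisions; up to 28 days = 672 h, with two systems, for chronic and dehisced wounds (6.1.1).
- Interruption figures: 24 h (7.8.1) and 48 h (9.1.4, 9.2.6, 10.1.4, 10.4.7).

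**Assumptions, because the protocol is silent**
- Criterion A is the subject's time average.
- Off-time enters that average as 0 mmHg.
- The two pumps of a 28-day subject are pooled.
- The pump runs at a constant pressure R; the main case is R = 80.

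**Formula.** With g hours lost out of H hours, mean = R × (1 − g/H). For R up to 86, A is met while the mean is at least 74, so the longest loss that passes is g = H × (1 − 74/R). At R = 80 this is 6/80 = 7.5% of the period.

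**Results at R = 80**
- 14 days: 24 h gives 80 × (1 − 24/336) = 74.29 (pass); 25 h gives 74.05 (pass); 26 h gives 73.81 (fail); 48 h gives 68.57 (fail).
- 28 days: 24 h gives 77.14 (pass); 48 h gives 80 × (1 − 48/672) = 74.29 (pass); 50 h gives 74.05 (pass); 72 h gives 71.43 (fail).

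**Longest loss that passes, by running pressure**

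| R (mmHg) | Full 14 days | Full 28 days, pooled |
|---|---|---|
| 79 | 21.3 h | 42.5 h |
| 80 | 25.2 h | 50.4 h |
| 80.2 | 26.0 h | 52.0 h |
| 82 | 32.8 h | 65.6 h |
| 86 | 46.9 h | 93.8 h |

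For a 24 h loss to pass over 14 days, R must be at least 74/(1 − 24/336) = 79.7. The same value applies to 48 h over 28 days, because the fraction lost is the same.

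**Shorter averaging periods at R = 80.** The limit is 7.5% of the hours averaged:
- 12.6 h at day 7 and 18.0 h at day 10.
- 21.6 h at day 12, the earliest day-14 visit.
- 45.0 h at day 25, the earliest day-28 visit.

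A 24 h loss passes only if at least 24/0.075 = 320 h (13.3 days) are averaged. A 48 h loss needs 48/0.075 = 640 h (26.7 days).

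**Changing the other assumptions**
- Each pump judged separately: a 50 h loss within one pump's 336 h gives 80 × (1 − 50/336) = 68.1 (fail).
- Off-time left out of the average: the mean equals R whatever g is, so a loss of any length passes.

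**The case against.** A reader might infer that any subject without vacuum for more than 24 hours scores as a success, and that the protocol regards such a subject as a treatment failure. The documents support neither reading.

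- Criterion A does not mention the average, so the link is an inference. This stands. But the average is the only subject-level pressure quantity that section 11 defines. If nominal means the rated pressure, every pump meets A by specification and the composite tests leakage alone. Either way A needs a definition.
- In a full 14-day subject at 80 mmHg, the losses that exceed 24 h and still pass span only 24 to 25.2 h. At 79 mmHg there are none. This stands.
- A subject withdrawn because of the loss has a shorter averaging period. If the loss is averaged in, a 24 h loss fails before about day 13.3. This stands, except that the loss disappears if discontinuation is dated to its start. Withdrawal is also only permitted, so subjects can continue after a long loss.
- Section 7.8.1 defines no failure, and other sections use 48 h. This stands.
- Pooling two pumps is an assumption, and 11.4 and 11.10 speak of 14 days. But 11.5 describes one average per subject from baseline to discontinuation, which favours pooling.
- The chip is said only to give delivery status, so time-stamped pressures cannot be taken for granted. This stands. The case report form is the assured source of durations.
- One could add that high and low pressures cancel. That is true as arithmetic, but nothing in the documents suggests that the pump runs far above 80 mmHg.
- The composite is not listed in 8.6.1 and has no success threshold. Reasons for dressing change, device deficiencies and treatment duration are summarised (11.6, 11.8), and section 11 promises a fuller SAP. This lowers the weight of the point, but none of those summaries measures the length of vacuum loss.

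**Conclusion.** The point holds in a limited form. The only planned pressure measure is a per-subject time average, criterion A is undefined for a subject, and recorded interruption durations go unused. If A is the average, off-time counts as 0 mmHg and the pump runs at 80 mmHg, losses of up to about 25 h (full 14 days) or about 50 h (full 28 days, pooled) can pass. The limits are about 21 h and 43 h at 79 mmHg, and about 33 h and 66 h at 82 mmHg.

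For closed incisions the practical effect is small unless off-time is excluded or the running pressure is above 80 mmHg. It matters mainly for chronic and dehisced wounds: four types with at least 10 subjects each (7.1), so at least 40 of the 70 planned. There a passing loss can exceed 24 h, and also 48 h if R is at least 79.7 mmHg over a full 28 days. The 24 h and 48 h passages conflict and must be reconciled. The point does not affect the validity of the TOST as a test of mean pressure. It is a cheap improvement that belongs in the SAP before database lock.

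**What to change.** Leave the TOST as it is, and add the following:

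1. Define criterion A as the subject's time-weighted average pressure with vacuum-off time counted as 0 mmHg. State how the two pumps of a 28-day subject are combined, where averaging stops for a subject withdrawn because of a vacuum loss, and whether shower disconnections count, since the removal form leaves them out.
2. Report total and longest vacuum loss per subject and by wound type, from the case report form and from the chip where it logs this.
3. Report Composite Clinical Success a second time, with A also requiring no vacuum loss longer than the interruption limit that the protocol retains once 7.8.1 is reconciled with the visit procedures and discontinuation forms.
4. Do not use ±6 mmHg as a tolerance for momentary readings without justification, because it was chosen as a margin for a mean. If the SD of 14.8 in 11.10 describes readings within one device (an assumption, with a normal distribution), a pump with the reference profile would be within ±6 of its mean only 2Φ(6/14.8) − 1, or about 31%, of the time. Any time-at-pressure summary should use the device's own therapy limits.

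The cost is a little more programming and a possibly lower composite success rate. The case report form already collects the durations needed, so no new data are required.
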